6.3 Efficacy

6.3.1 Efficacy variables

The primary efficacy variable, cardiac troponin I at 24 hours post-PCI will be determined according to local standard clinical practice. In detail, cTnI will be analyzed with an automated immunoassay (Bayer ADVIA IMS Troponin-I Ultra method, Bayer, Berlin, Germany). The 99th percentile of the cTnI level in a reference population (upper reference limit, URL) of healthy volunteers was below the lower limit of detection of 0.04 ng/mL. The coefficient of variation (CV) of the assay was <10%, complying with the recommendations of the European Society of Cardiology (ESC)/ American College of Cardiology (ACC)/ American Heart Association (AHA) for optimal precision. The analytical range was 0.01 to 50ng/mL, with an assay sensitivity of 0.006 ng/mL.

Chest pain during PCI is a secondary efficacy variable. It will be assessed during the post-PCI clinical examination of the subject by the investigator or by an appropriately qualified person to whom the investigator has delegated this duty. An analog 10 point scale will be used (0: no pain, 10: most severe discomfort ever experienced).

ST-segment deviation during balloon occlusion will be monitored as a secondary efficacy variable. It will be defined as the absolute value of ST-segment deviation at 60-80ms after the J-point in mm at the beginning of coronary angiography minus ST-segment deviation at 60-80ms after the J-point in mm during balloon occlusion.

6.4 Safety

The Principal Investigator is responsible for ensuring that all staff involved in the study is familiar with the content of this section.

6.4.1 Definition of adverse events

An adverse event (AE) is defined as any untoward medical occurrence in a patient or clinical study subject administered a medicinal product and which does not necessarily have a causal relationship with this treatment. An AE can therefore be any unfavorable and unintended sign (eg, tachycardia, enlarged liver, or an abnormal laboratory finding), symptom (eg, nausea, chest pain), or disease temporally associated with the use of a study drug, whether or not considered related to the study drug. In clinical studies, an AE can include an undesirable medical condition occurring at any time, including run-in or washout periods, even if no study treatment has been administered.

The term AE is used to include both serious and non-serious AEs.

6.4.2 Definitions of serious adverse event

A serious adverse event is an AE occurring during any study phase (ie, run-in, treatment, washout, follow-up), that fulfils one or more of the following criteria:

- Results in death
- Is immediately life-threatening
- Requires in-patient hospitalization or prolongation of existing hospitalization
- Results in persistent or significant disability/incapacity or substantial disruption of the ability to conduct normal life functions
- Is a congenital abnormality or birth defect
- Is an important medical event that may jeopardize the subject or may require medical intervention to prevent one of the outcomes listed above.

The causality of SAEs (their relationship to all study treatment/procedures) will be assessed by the investigator(s) and communicated to AstraZeneca.

6.4.3 Recording of adverse events

Time period for collection of adverse events

Adverse Events will be collected from the time of signature of informed consent throughout the study treatment period (including the 30-day follow-up period post-PCI), up to 30 days after randomization.

SAEs will be recorded from the time of informed consent and up to 30 days after randomization.

Follow-up of unresolved adverse events

Any AEs that are unresolved at the subject's last AE assessment in the study are followed up by the Investigator for as long as medically indicated, but without further recording in the CRF. Sponsor or its designee retains the right to request additional information for any subject with ongoing AE(s)/SAE(s) at the end of the study, if judged necessary.

Variables

The following variables will be collect for each AE;

1. AE (verbatim)
2. The date and time when the AE started and stopped
3. Severity

Note: the following severity rating scale will be used:

- *mild* (awareness of sign or symptom, but easily tolerated for outpatients, and awareness of sign or symptom, but easily tolerated for in-patients)
- *moderate* (discomfort sufficient to cause interference with normal activities for outpatients, and disturbing but still tolerable for in-patients)
- *severe* (incapacitating, with inability to perform normal activities for outpatients, and intolerable for outpatients)

4. Whether the AE is serious or not
5. Investigator causality rating against the Investigational Product (not related, possible, or probable)
6. Action taken with regard to investigational product(s)
7. AE caused subject's withdrawal from study (yes or no)
8. Outcome.

In addition, the following variables will be collected for SAEs:

1. Date AE met criteria for serious AE
2. Date Investigator became aware of serious AE
3. AE is serious due to
4. Date of hospitalisation
5. Date of discharge
6. Probable cause of death
7. Date of death
8. Autopsy performed
9. Causality assessment in relation to Study procedure(s)
10. Causality assessment in relation to Other medication
11. Description of AE.

It is important to distinguish between serious and severe AEs. Severity is a measure of intensity whereas seriousness is defined by the criteria in Section 6.4.2. An AE of severe intensity need not necessarily be considered serious. For example, nausea that persists for several hours may be considered severe nausea, but not a SAE. On the other hand, a stroke that results in only a limited degree of disability may be considered a mild stroke but would be a SAE.

The Sponsor or its designee will classify events using Medical Dictionary for Regulatory Activities (MedDRA).

Causality collection

The Investigator will assess causal relationship between Investigational Product and each Adverse Event, and answer ‘yes’ or ‘no’ to the question ‘Do you consider that there is a reasonable possibility that the event may have been caused by the investigational product?’.

For SAEs causal relationship will also be assessed for other medication and study procedures. Note that for SAEs that could be associated with any study procedure the causal relationship is implied as ‘yes’.

Adverse Events based on signs and symptoms

All AEs spontaneously reported by the subject or reported in response to the open question from the study personnel: <<‘Have you had any health problems since you were last asked?’>> or revealed by observation will be collected and recorded in the CRF. When collecting AEs, the recording of diagnoses is preferred (when possible) to recording a list of signs and symptoms. However, if a diagnosis is known and there are other signs or symptoms that are not generally part of the diagnosis, the diagnosis and each sign or symptom will be recorded separately.

Adverse Events based on examinations and tests

The results from protocol mandated laboratory tests and vital signs will be summarized in the clinical study report. Deterioration as compared to baseline in protocol-mandated laboratory values and vital signs should therefore only be reported as AEs if they fulfil any of the SAE criteria or are the reason for discontinuation of treatment with the investigational product.

If deterioration in a laboratory value/vital sign is associated with clinical signs and symptoms, the sign or symptom will be reported as an AE and the associated laboratory result/vital sign will be considered as additional information. Wherever possible the reporting Investigator uses the clinical, rather than the laboratory term (eg, anaemia versus low haemoglobin value). In the absence of clinical signs or symptoms, clinically relevant deteriorations in non-mandated parameters should be reported as AE(s).

Deterioration of a laboratory value, which is unequivocally due to disease progression, should not be reported as an AE/SAE.

Any new or aggravated clinically relevant abnormal medical finding at a physical examination as compared with the baseline assessment will be reported as an AE.

Disease progression or worsening of pre-existing conditions

Disease progression can be considered as a worsening of a subject's condition attributable to the disease (i.e., STEMI) for which the investigational product is being studied.

It may be an increase in the severity of the disease under study and/or increases in the symptoms of the disease. The development of ischaemia and symptoms of coronary artery disease, artery disorders, cardiac failure, pericardium disorders, arrhythmias and other MI-related cardiac symptoms/disorders should be considered as disease progression and not an AE.

Events, which are unequivocally due to disease progression, should not be reported as an AE during the study.

Worsening of the disease under study will be recorded as an AE only if one of the following criteria is met:

- *Worsening of disease meets the criteria for an SAE.*
- *Action is taken with investigational drug, i.e. dose is reduced or treatment discontinued or increased.*
- *Concomitant medication is added or changed.*
- *The investigator believes a subject has shown a clear, unexpected deterioration from baseline symptoms.*

The same criteria as above apply for the recording of AEs that result from worsening of other pre-existing diseases/conditions. In particular, the following will not qualify for recording as an AE:

- *Pre-existing conditions present at baseline, which remain unchanged during the study.*
- *Expected fluctuations or expected deterioration of a pre-existing disease/condition.*

Reporting of serious adverse events

The Sponsor and Principal Investigator are responsible for meeting all local regulatory requirements and obligations.

All SAEs have to be reported, whether or not considered causally related to the investigational product, or to the study procedure(s). All SAEs will be recorded on the SAE page as well as on the relevant AE module of the pCRF.

If any SAE occurs in the course of the study, then Investigator or other site personnel should inform the Sponsor or its designee immediately, or **no later than 24 hours** from awareness of the event.

The Sponsor or its designee will work with the Investigator to ensure that all the necessary information is provided to the Safety database, as appropriate.

For fatal or life-threatening adverse events where important or relevant information is missing, active follow-up is undertaken immediately. Investigator or other site personnel should inform

the Sponsor or its designee of any follow-up information on a previously reported SAE immediately, or **no later than 24 hours** from awareness of the event.

Investigator or other site personnel send relevant SAE form by fax or e-mail (scanned copies) to the Sponsor or its designee.

The reference documents for definition of expectedness of an AE is the investigational products' latest approved prescribing information (SmPCs).

The Sponsor or its designee is responsible for reporting to the National Ethics Committee and the European Medicines Agency (EMA), of the Serious Unexpected Suspected Adverse Drug Reactions (SUSARs) occurring in the study, including SUSARs associated with active comparator(s).

SUSARs are forwarded electronically by the Sponsor or its designee to Receiver ID "EVCTMPROD" in the production environment of Eudravigilance.

The reporting timelines are the following:

- Fatal or life-threatening SUSARs: within 7 days of Sponsor's (or its designee) date of awareness
- All other SUSARs within 15 days of Sponsor's (or its designee) date of awareness.

Sponsor's or its designee contact details are the following:

Name of Responsible Person: [name]

Address: [name]

[contact]

Mob.: [name]

[contact]

E-mail: [contact]

The Sponsor or its designee or the Principal Investigator is required, to notify AstraZeneca of all SUSARs, as soon as possible and at least at the same time that the reports are sent to the Eudravigilance. Reports should be sent to AstraZeneca on a CIOMS form to the following e-mail address: <[contact] .

In addition, the Principal Investigator must provide AstraZeneca with the same report of all other SAEs that did not qualify for expedited reporting at the same e-mail address and on an expedited basis. These reports must be submitted to AstraZeneca quarterly.

The Sponsor or its designee when providing local periodic study reports to the local Regulatory Authority and any IRB/IEC updates shall at the same time forward a copy of such documentation to AstraZeneca.

The Principal Investigator is responsible for reconciling the clinical data of the ISS on an ongoing basis to ensure that all new and updated information regarding SAEs has been sent to AstraZeneca either as individual expedited SUSARs or as part of a line listing.

The Sponsor shall ensure that safety information provided by AstraZeneca is promptly distributed to local Regulatory Authority, National Ethics Committee and to any other Investigators participating in the ISS, in accordance with Applicable Laws and Regulations.

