6.4.4 Laboratory safety assessment

Daily tests for hemoglobin, complete blood count including platelet count, serum creatinine, AST, ALT, INR, cardiac Troponin I on Day 1, Day 2, and Day 3.

For blood volume see Section 7.1.

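### Section 6.4.3 keeps a laboratory deterioration attributed to disease progression out of SAE reporting even when it is serious, which conflicts with the neighbouring SAE rules; the gap is narrow but should be closed

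*Combined protocol and SAP*

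**What the plan says.** All the rules at issue except the seriousness criteria and the laboratory schedule stand in Section 6.4.3 of the combined protocol and SAP.

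- **Mandated laboratory values** (under examinations and tests). A deterioration from baseline "should therefore only be reported as AEs if they fulfil any of the SAE criteria" or if it leads to stopping the study drug.
- **Laboratory change attributed to progression** (same subsection). "Deterioration of a laboratory value, which is unequivocally due to disease progression, should not be reported as an AE/SAE". Nothing is said about seriousness.
- **Laboratory change with signs or symptoms** (same subsection). The clinical finding is the AE, and the laboratory result is supporting information.
- **Disease progression**. Ischaemia, coronary symptoms and MI-related disorders count as progression. "Worsening of the disease under study will be recorded as an AE only if one of the following criteria is met"; the first criterion is "Worsening of disease meets the criteria for an SAE".
- **SAE reporting**. Every SAE goes to the sponsor within 24 hours of awareness, whatever its cause.

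Section 6.4.2 defines an SAE as an AE that meets at least one seriousness criterion, among them "Requires in-patient hospitalization or prolongation of existing hospitalization". Section 6.4.4 makes troponin one of the mandated safety tests: "AST, ALT, INR, cardiac Troponin I on Day 1, Day 2, and Day 3".

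**The concern.** The laboratory sentence is the only progression rule that names SAEs in its exclusion, and it has no route back for a serious case. A site that treats it as the more specific instruction would withhold an event that the adjacent rules want notified within 24 hours.

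This touches the trial's own subject. Troponin is measured on Days 1 to 3 and is the primary efficacy variable. Progression is defined broadly enough to take in ischaemia and MI-related disorders. Treatment is open label. Section 5.3 gives the two blinded assessors the ST-segment readings, and no blinded review of attribution to progression is described. At stake are the completeness of the SAE record, the 24-hour notice to the sponsor and the quarterly SAE reports to the drug manufacturer. The descriptive SAE counts could also be recorded unevenly between arms.

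**Working it through.** The plan states no figure on this point and no arithmetic applies. The check is to take one event through each rule.

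**Test event.** After PCI, troponin rises on a mandated sample. The patient has no symptoms or signs, but the stay is prolonged because of the rise. The investigator judges it unequivocally due to disease progression.

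1. *Section 6.4.2.* Prolonged hospitalisation is a seriousness criterion, so the event is serious if it counts as an AE.
2. *Section 6.4.3, mandated laboratory values.* Troponin is mandated (Section 6.4.4) and an SAE criterion is met. Result: reportable.
3. *Section 6.4.3, laboratory change attributed to progression.* The condition is met as judged. Result: not reported as an AE and not reported as an SAE.
4. *Section 6.4.3, disease progression.* The judgement that triggers step 3 also makes the event a worsening of the disease. It meets the first criterion on the list. Result: recorded.
5. *Section 6.4.3, SAE reporting.* All SAEs are reported regardless of causality. Result: reportable within 24 hours, if the event is accepted as an AE.

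Steps 2 and 4 contradict step 3 directly. Step 5 contradicts it less firmly: an SAE is by definition an AE, so a site could say that step 3 removes the event before step 5 applies.

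**Variations that mark the edge of the gap.**

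- *Add symptoms or signs.* The clinical finding becomes the AE and the troponin result supports it. If the event is serious, the exception in the disease-progression list and the SAE rule both apply. The laboratory sentence is not needed to decide the case.
- *Remove the certainty about cause.* The sentence applies only when progression is unequivocal. If the investigator thinks the procedure may have contributed, step 3 drops out and step 2 decides.
- *Remove seriousness.* No SAE is at issue.

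Only the test event as first described is caught: an isolated laboratory change that meets a Section 6.4.2 criterion and is attributed without doubt to progression.

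**A further ambiguity.** The progression definition names the disease under study as STEMI. Section 4 describes patients with stable CAD or NSTEMI-ACS, and inclusion criterion 3 in Section 4.1 names NSTEMI-ACS. The term on which step 3 turns is therefore tied to a condition that the trial does not enrol.

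**The case against.** The strongest reply is that the sentence will seldom decide anything.

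- *A post-PCI troponin rise is hardly ever unequivocal progression.* Section 1.1 describes peri-procedural injury as arising from the procedure, through side-branch occlusion or distal embolism. Section 6.4.3 presumes a causal link for SAEs that could be associated with a study procedure. This stands, and it narrows the gap. It does not close it, because the broad progression definition still lets an investigator make the attribution.
- *The values are not lost.* Troponin at 24 hours is the primary variable, CRFs are fully source-verified (Section 6.1), and mandated laboratory results are summarised in the study report. This stands. What can be lost is the SAE record and its prompt notification.
- *No planned test is affected.* The only safety comparison specified in Section 12.2 is TIMI bleeding by Fisher's exact test. This stands.
- *The exclusion is a legitimate carve-out, since an SAE must first be an AE.* This weakens the conflict with the SAE reporting rule. It does not answer the conflict with the mandated-laboratory rule or with the disease-progression list.

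A reader might infer more: that serious post-PCI infarctions in general can drop out of safety reporting. The documents do not support that. The sentence concerns a laboratory value, and a clinical event that meets a seriousness criterion stays recordable and reportable by other rules in the same section.

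**Conclusion.** The inconsistency is real and is in the current text. As written, the laboratory sentence tells a site to withhold a serious laboratory event that two neighbouring rules clearly make recordable or reportable and that a third, read with them, sends to the sponsor within 24 hours. Its reach is limited to the isolated, serious, progression-attributed laboratory change. The primary analysis and the planned bleeding comparison are untouched.

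Its size cannot be derived from the documents. A reader might apply the 20% to 45% incidence of peri-procedural injury in Section 1.1 to the planned sample: 0.20 × 152 = 30.4 and 0.45 × 152 = 68.4. With the 15% dropout allowance removed, 0.85 × 152 = 129.2, which gives 0.20 × 129.2 = 25.8 and 0.45 × 129.2 = 58.1. These are not counts of affected events. The incidence is for elective procedures and covers any biomarker-detected injury. Three further shares would be needed: how many rises meet a seriousness criterion, how many of those come without a reportable clinical event, and how many are judged unequivocally due to progression. The documents give none of them.

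The conclusion rests on the wording alone and on the assumption that sites read the sentence literally.

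**What to change.** Make two changes to Section 6.4.3.

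1. Delete /SAE from the laboratory sentence and add: *unless it meets a criterion in Section 6.4.2, in which case it is reported as an SAE*. The sentence then agrees with the mandated-laboratory rule, the disease-progression list and the SAE reporting rule.
2. Reconcile the disease named in the progression definition (STEMI) with the population in Sections 4 and 4.1, so that sites know what progression means in this trial.

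The cost is a short amendment, approved before use as Section 8.4 requires, and possibly a few more SAE forms. No treatment, endpoint, analysis or sample size changes.

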6.4.6 ECG

6.4.6.1 Resting 12-lead ECG

On Day 1 and Day 2. Furthermore, whenever it is considered appropriate according to symptoms and physical findings. Particular inspection for bradycardia, conduction disturbances, ventricular pauses.

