13. IMPORTANT MEDICAL PROCEDURES TO BE FOLLOWED BY THE INVESTIGATOR

13.1 Overdose

There is currently no known antidote to reverse the effects of ticagrelor, and ticagrelor is not expected to be dialyzable. Treatment of overdose should follow local standard medical practice.

The expected effect of excessive ticagrelor dosing is prolonged duration of bleeding risk associated with platelet inhibition. If bleeding occurs, appropriate supportive measures should be taken.

Ticagrelor is well tolerated in single doses up to 900 mg. Gastrointestinal toxicity was dose-limiting in a single ascending dose study. Other clinically meaningful adverse effects which may occur with overdose include dyspnoea and ventricular pauses.

In the event of overdose, observe for these potential adverse effects and consider electrocardiogram monitoring.

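### Section 6.4.3 presumes arrhythmias to be disease progression, so a non-serious, untreated rhythm finding on the safety ECGs need not be recorded as an adverse event

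*Combined protocol and SAP*

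**What the plan says.** Section 6.4.6.1, in the safety chapter, schedules a resting 12-lead ECG on Day 1 and Day 2, with more if symptoms or findings call for them. It asks for: "Particular inspection for bradycardia, conduction disturbances, ventricular pauses".

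Section 6.4.3 describes disease progression as worsening "attributable to the disease (i.e., STEMI) for which the investigational product is being studied". It lists several kinds of cardiac event and ends by saying that "arrhythmias and other MI-related cardiac symptoms/disorders should be considered as disease progression and not an AE". The sentence after that bars reporting only of events that are *unequivocally* progression. Then: "Worsening of the disease under study will be recorded as an AE only if one of the following criteria is met". The criteria are:

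- "Worsening of disease meets the criteria for an SAE";
- "Action is taken with investigational drug, i.e. dose is reduced or treatment discontinued or increased";
- a concomitant medication is started or altered;
- the investigator judges that the patient has worsened clearly and unexpectedly, measured against symptoms at baseline.

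On tests, the same section says that worsening laboratory values and "vital signs should therefore only be reported as AEs if they fulfil any of the SAE criteria", or if they are why the investigational product was stopped. The reason given is that these results are summarised in the study report. A new, clinically relevant abnormality at physical examination, by contrast, is an AE.

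Section 6.4.1 defines AEs broadly and uses tachycardia as an example. Section 13.1 states: "Other clinically meaningful adverse effects which may occur with overdose include dyspnoea and ventricular pauses".

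**The concern.** The protocol asks sites to look for three rhythm findings as a safety matter, then gives a default rule that attributes arrhythmias to the disease. A site that follows section 6.4.3 literally can see such a finding and properly leave it off the AE page.

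Two things are at stake. First, the causality question in section 6.4.3 is put only for AEs. An event classed as progression is never assessed for a link to the drug, so the rule settles causality before anyone asks. Second, bleeding is the only safety variable derived in section 11.2 and the only one tested in section 12.2. What the trial learns about rhythm must therefore come mainly from AE records, and section 1.4 relies on a month of AE monitoring when it weighs benefit against risk.

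The reference to STEMI adds to the difficulty. Section 4 recruits stable coronary disease or non-ST-elevation ACS, and section 4.1 lists only the latter. Sites have no definition of progression that fits the patients enrolled.

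**Working it through.** No arithmetic applies. The check takes one case and follows it through every recording route in the protocol: a new conduction disturbance or pause on the Day 2 ECG, non-serious, without symptoms, with no change to the study drug or other medication.

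1. **General definition (6.4.1).** The finding fits: it is an unfavourable sign, and a link to the drug is not required.
2. **Progression default (6.4.3).** Arrhythmias are classed as progression. On a literal reading, the case leaves AE recording here.
3. **The four criteria for return (6.4.3).** Seriousness: not met. Study-drug action: not met. Medication change: not met. Clear, unexpected worsening: not met, because the test is tied to symptoms and there are none. The last three can each bring in a non-serious event, but not this one.
4. **Physical-examination rule (6.4.3).** This can catch a slow or irregular pulse. It does not reach a finding visible only on the tracing. For heart rate it also competes with the vital-sign rule, which restricts AE reporting.
5. **Findings without symptoms (6.4.3).** Clinically relevant deterioration is reportable in parameters that the protocol does not mandate. The Day 1 and Day 2 ECGs are mandated, so a finding on them falls outside this rule. The restriction on mandated tests names laboratory values and vital signs, not ECGs, so no sentence on tests clearly governs the case.
6. **Data capture (6.2).** ECGs are listed among the data collected at screening and after the procedure, so the tracing is not lost.
7. **Reporting (6.4.3, 11.2, 12.1, 12.2).** The promised report summary covers laboratory tests and vital signs. Section 12.1 says in general terms that all variables will be described, but no ECG or rhythm variable is defined. Only bleeding is derived and tested.
8. **Who decides (5.3).** The study is open label. The blinded assessors judge outcomes, specifically ST-segment deviation. Nothing provides for a blinded decision between progression and AE.

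Result: the case can pass every route without becoming an AE, without a causality rating and without a specified place in the report.

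**The case against.** The strongest reply is that section 6.4.3, read as a whole, already limits itself. Progression means worsening attributable to the disease; the list can be read as covering only MI-related arrhythmias; and only unequivocal progression is barred from reporting. A pause that might be drug-related is not unequivocal progression, so a careful investigator could report it. That reading is available, but the sentence classing arrhythmias as progression carries no such condition. Sites are left with two instructions that can give different answers.

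Several stronger readings are tempting, and the reply defeats them:

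- *All non-serious bradycardia, conduction disturbance and pauses go unrecorded.* Not so. Three of the four criteria, the physical-examination rule and the unequivocal-progression qualifier can each bring in non-serious events. Symptoms that accompany a vital-sign change are also reported as AEs.
- *A low heart rate disappears.* Not so. Vital-sign results are to be summarised in the study report.
- *The ECG inspection leaves no record.* Not so. Section 6.2 has the ECG collected. What is missing is a specified summary.
- *The protocol says that ticagrelor causes pauses at study doses.* It does not. Section 13.1 speaks of overdose, and section 6.4.6.1 only asks for inspection. The documents therefore do not show that an undercount would favour ticagrelor.

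It is also fair that serious events are captured in full and that no planned test changes.

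**Conclusion.** The conflict between sections 6.4.3 and 6.4.6.1 is real, and it comes from a stated rule, not from silence. It affects a defined subset: non-serious rhythm findings with no study-drug action, no medication change and no clear, unexpected symptomatic worsening, typically seen only on ECG. These need not be recorded as AEs or assessed for causality, and no ECG summary is specified. Because allocation is known, the classification could differ between arms; the documents do not establish that it would, or in which direction.

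The number of events cannot be given. The planned ticagrelor group is 152 / 2 = 76 patients, but the documents contain no rate for such findings. An assumed rate would not measure the loss. The conclusion rests on sites applying the arrhythmia sentence as written. It does not touch the primary analysis, the secondary efficacy measures or the TIMI bleeding comparison. The text should be corrected because the gap concerns findings that the protocol itself tells sites to look for.

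**What to change.** Reconcile sections 6.4.3 and 6.4.6.1 as follows:

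- State in 6.4.3 that new, clinically relevant bradycardia, conduction disturbance or ventricular pauses are not presumed to be disease progression, and are recorded as AEs with a causality rating whether or not serious. Keeping clinical relevance as the threshold matches the standard already used elsewhere in that section.
- Say that this holds however the finding arises (ECG, procedural monitoring, vital signs or examination), so that the vital-sign restriction does not override it.
- Replace STEMI with the conditions actually enrolled.
- Add to section 12.2 a table of these events by drug arm. A descriptive count is enough.

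The change takes a few sentences and one table, with no new test or visit. The downside is slightly more AE recording, including some events that will prove to be due to the disease; the causality rating is the place to say so.
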